### 2.2.1 Subgroups of interest

The following subgroups will be analyzed for the primary endpoint and for selected secondary endpoints based on clinical decision:

1. Age group ( $< 65, \geq 65$  years) and ( $< 75, \geq 75$  years)
2. Left ventricular ejection fraction (LVEF) categories prior to randomization:
  - $> 40$  to  $< 45\%$  vs.  $\geq 45\%$ ;

- > 40 to < 50% ((HFmrEF (mildly reduced) ), ≥ 50% ( (HFpEF) preserved )
- ≥ 50 to ≤ 60% vs. >60\*
- >40 to ≤60 vs. > 60\*
- ≤ median vs. > median

3. Prior use of ACEi/ARB (at the time of hospitalization)
4. Four groups defined by the Baseline quartiles of NT-proBNP
5. Baseline eGFR (< 45, 45 to < 60, ≥ 60 ; <30 or ≥ 30 mL/min/1.73 m^2)
6. SBP at randomization (< 110, ≥ 110 mm Hg)
7. Race
8. Ethnicity
9. Atrial fibrillation (AF) vs. no AF at the time of consent
10. Body mass index (BMI) ≥ 30 vs. BMI < 30; BMI ≤50 vs. >50 kg/m^2
11. Sex
12. New onset HF (at the time of hospitalization) – ‘de novo heart failure’
13. New York Heart Association (NYHA) class at randomization
14. Recovered EF / Improved EF (HFimpEF) (most recent left ventricular ejection fraction (LVEF) > 40% (within past 3 months), but history of prior documented LVEF < 40%)
15. Time from presentation to hospital (if applicable) to randomization time
16. Prior history of HF
17. Prior Hospitalization for Heart Failure
18. Duration of Heart Failure (< 12 months, 12-24 months, 24-60 months, and > 60 months)
19. In-hospital/out-of-hospital randomization status
20. Structural heart disease (yes/no)
21. Subjects without COVID-19 positive during the trial.
22. Enrollment Country: Canada vs United States

\* LVEF of >60% is defined as normal; LVEF <= 60% is defined as “below normal”

See [Sections 2.5](#) and [2.6](#) for further details on the primary and secondary objectives, respectively.

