
To assess the effect of sacubitril/valsartan vs. valsartan on the incidences of a composite endpoint of worsening renal function (renal death, reaching ESRD, or decline in eGFR $\geq 50\%$)	
The incidences of a composite endpoint of worsening renal function, defined as:
renal deathreaching end-stage renal disease (ESRD)$\geq 50\%$ decline in estimated glomerular filtration rate (eGFR) relative to baseline

To assess the effect of sacubitril/valsartan vs. valsartan on	
Proportional change in NT-proBNP from baseline to Week 8

Objective(s)	Endpoint(s)
change in NT-proBNP from baseline to Week 8	
• To assess the effect of sacubitril/valsartan vs. valsartan on change from baseline in hs-Troponin (high sensitivity) at Weeks 4 and 8
	
• Proportional change from baseline in hs-Troponin (high sensitivity) at Weeks 4 and 8• To assess the effect of sacubitril/valsartan vs. valsartan on tolerability and the incidence of adverse events of special interest during treatment• Dosing levels and discontinuations• Incidence of symptomatic hypotension during treatment• Incidence of hyperkalemia (potassium >5.5 mEq/L)• Incidence of angioedema• Incidence of worsening renal function, defined as an increase in serum creatinine of ≥ 0.5 mg/dl and worsening of the eGFR by at least 25%

3 Study design

Figure 3-1 Study Design

*The maximum duration of study for the first patient randomized after the amendment is approximately 84 weeks (20 months) when the last patient randomized is treated for 8 weeks (2 months). The average duration of study for all patients is approximately 46 weeks (11 months).

This study will use a randomized, double-blind, double-dummy, active-controlled, parallel group design. Eligible patients will be randomized either during hospitalization for, or within 30 days of, a WHF event (HFpEF decompensation). A WHF event (HFpEF decompensation) is defined as a hospitalization, emergency department (ED) visit or out-of-hospital urgent HF visit, all requiring IV diuretics.

Randomized patients will have been hemodynamically stabilized defined in this study as:

- SBP \geq 100mmHg for the preceding 6 hours prior to randomization; no symptomatic hypotension

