14. Clinically significant congenital heart disease felt to be the cause of the patient's symptoms and signs of HF
15. Coronary or carotid artery disease or valvular heart disease likely to require surgical or percutaneous intervention within the duration of the trial
16. Any surgical or medical condition, which in the opinion of the investigator, may place the patient at higher risk from his/her participation in the study, or is likely to prevent the patient from complying with the requirements of the study or completing the study
17. Known hepatic impairment (as evidenced by total bilirubin > 3 mg/dL, or increased ammonia levels, if performed), or history of cirrhosis with evidence of portal hypertension such as varices
18. Participation in any other clinical trial involving investigational agents or devices within the past 30 days
19. Current confirmed COVID19 infection
20. Past COVID19 infection with persistent symptom burden suspected due to COVID19
 - Persistent symptoms may include, but are not limited to, continued cough, breathing difficulty, muscle/joint aches, and gastrointestinal symptoms from the time of COVID19 infection onward.
21. Pregnant or nursing (lactating) women, where pregnancy is defined as the state of a female after conception and until the termination of gestation, confirmed by a positive hCG laboratory test.
22. Women of child-bearing potential, defined as all women physiologically capable of becoming pregnant, unless they are using highly effective methods of contraception during dosing of investigational drug and for 7 days off of study drug. Highly effective contraception methods include:
 - Total abstinence (when this is in line with the preferred and usual lifestyle of the patient. Periodic abstinence (e.g., calendar, ovulation, symptothermal, post-ovulation methods) and withdrawal are not acceptable methods of contraception
 - Female sterilization (have had surgical bilateral oophorectomy with or without hysterectomy) or tubal ligation at least six weeks before taking study treatment. In case of oophorectomy alone, only when the reproductive status of the woman has been confirmed by follow-up hormone level assessment

- Male sterilization (at least 6 months prior to Visit 1). For female patients on the study, the vasectomized male partner should be the sole partner for that patient

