Patients should be seen for all visits/assessments as outlined in the assessment schedule ([Table 8-1](#)) or as close to the designated day/time as possible. Missed or rescheduled visits should not lead to automatic discontinuation. Patients who prematurely discontinue the study for any reason should be scheduled for a visit as soon as possible, at which time all of the assessments listed for the final visit will be performed. At this final visit, all dispensed investigational product should be reconciled, and the adverse event and concomitant medications recorded on the CRF.

If the COVID-19 pandemic limits or prevents on-site study visits, alternative methods of providing continuing care may be implemented. Virtual visits [e.g. phone calls, video visits (preferred)] or visits by site staff/home nursing service to the participant's home

depending on local regulations and capabilities, can replace on-site study visits, for the duration of the pandemic until it is safe for the participant to visit the site again.

Table 8-1 Assessment Schedule

Period	Screening	Double-Blind Treatment (84 week)									
Visit Name	Screening	Randomizati on/Baseline									Study Completion/ End of Study
Visit Number	Visit 1	Visit 2	Visit 3	Visit 5	Visit 7	Visit 11	Visit 13	Visit 15	Visit 16	Visit 17	
Week (Day)	[Day -30 to -1.5 (36hours)]	0 (Day 1)	1 (Day 7)	4 (Day 28)	8 (Day 56)	24 (Day 168)	40 (Day 280)	56 (Day 392)	68 (Day 476)	84 (Day 588)	

X = assessment to be recorded in the clinical database or received electronically from a vendor
S = assessment to be recorded in the source documentation and in the database
H = assessment to be recorded in the source documentation and in the database

² All female patients of childbearing potential will have a serum pregnancy test (hCG) performed at Visit 1 (local lab). A urine pregnancy test will be conducted in the local laboratory for remaining visits

⁴ CV medications will be recorded at time of hospital discharge.

⁵ BNP or NT-proBNP will be assessed at Visit 1 via local laboratory. Only NT-proBNP will be assessed via central laboratory for Visits 2, 3, 5 and 7.

⁶ Health status phone call 4 weeks after study completion.

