### **2.5    Analysis of the primary objective**

#### **2.5.1    Primary endpoint**

The primary endpoint is the comparison of the time-averaged proportional change from Baseline in NT-proBNP between sacubitril/valsartan and valsartan to Week 4 and 8.

Primary analysis timepoint will be the change from Baseline to averages of Week 4 and 8.

The analysis of the primary endpoint will be based on the FAS.

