### **2.5.6 Sensitivity analyses 3**

A third sensitivity analysis will be performed by excluding assessments after COVID-19 positive status at the subject level. The analysis will be performed similar to the main analysis of the primary endpoint.

The sensitivity analysis to address the primary objective will be based on the same primary estimand.

The analysis will be performed based on all available data in the FAS. Missing values caused due to unevaluable samples or early discontinuations will not be imputed.

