### **2.5.9 Subgroup analyses**

All subgroups as defined in [Section 2.2.1](#) will be analyzed for the primary endpoint.

The subgroup analysis will be based on the same primary estimand.

- The analyses will be performed like the main analysis of the primary endpoint with the addition of an interaction term for the subgroup and treatment.

An interaction p-value will be generated from a likelihood ratio test comparing the interaction model to the model without the interaction.

- Forest plots will be produced including interaction p-values for treatment by subgroup interactions.

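### SAP 2.2.1 item 21 is a post-randomization COVID-19 subgroup with no time limit and no stated complement, yet it gets an interaction test on the Week 4/8 primary endpoint

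*SAP*

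**What the plan says.** SAP 2.2.1 opens its list with "The following subgroups will be analyzed for the primary endpoint and for selected secondary endpoints based on clinical decision". Items 1 to 20 and item 22 are known at or before randomization: age, LVEF, prior ACEi/ARB use, baseline NT-proBNP and eGFR, SBP and NYHA class at randomization, country and so on. Item 21 reads "Subjects without COVID-19 positive during the trial". It names one level only and gives no date or visit after which a positive result stops counting.

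SAP 2.5.9 applies the whole list to the primary endpoint. It repeats the primary ANCOVA "with the addition of an interaction term for the subgroup and treatment", takes an interaction p-value from a likelihood ratio test, and shows the results in forest plots.

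The outcome is complete early. SAP 2.5.1 states: "Primary analysis timepoint will be the change from Baseline to averages of Week 4 and 8". The footnote to the assessment schedule (Protocol Table 8-1) states: "Only NT-proBNP will be assessed via central laboratory for Visits 2, 3, 5 and 7". Visit 7 is Week 8. Follow-up continues well beyond that for most of the design: at least 8 weeks, up to about 84 weeks, and 46 weeks on average according to the note under Protocol Figure 3-1.

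COVID-19 is also handled elsewhere. Sensitivity analysis 3 (SAP 2.5.6) repeats the primary analysis while "excluding assessments after COVID-19 positive status at the subject level". SAP 2.6.2 adds analyses of the secondary endpoints that censor data after a COVID-19 diagnosis.

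**The concern.** A subgroup interaction asks whether the treatment effect differs between kinds of patient who could be told apart at baseline. Item 21 cannot answer that question, because the label is assigned by what happens during follow-up. Protocol 5.2 excludes "Current confirmed COVID19 infection", so a positive status in the trial is in practice a post-randomization one.

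The missing time limit makes this worse. A patient first positive at Week 60 carries the positive label in a comparison of NT-proBNP that closed at Week 8. That infection cannot have altered the measurement.

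Membership also reflects matters other than infection:

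- **Survival and follow-up.** A patient who dies or leaves at Week 10 has had little chance to test positive and so tends to count as COVID-free.
- **Enrolment era.** The full analysis set pools all protocol versions, and SAP 2.1.1 recognizes patients who finished before the pandemic start date of 01-Mar-2020. They would be counted as COVID-free because of when they enrolled.

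If the subgroup is carried to the clinical secondary endpoints, as SAP 2.2.1 allows, the outcome itself decides membership in part: an early CV death ends the time in which a patient could turn positive.

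At stake is one interaction p-value and one forest-plot row that a reader would take at face value beside properly defined baseline subgroups.

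**Working it through.** **1. The plan's own figures.** The 46-week average agrees with the stated minimum and maximum if follow-up is spread evenly between them: (8 + 84)/2 = 46. SAP 1.1 dates the 11-month projection to modeling from December 2019, when the target was 800 patients rather than the present 450, so it is a projection and may not match what occurs. The stated power also reproduces: 450 × 0.85 / 2 ≈ 191 evaluable per arm; 0.2614 / (0.85 × √(2/191)) = 3.005; 3.005 − 1.960 = 1.045; power = Φ(1.045) = 85.2%, against 85%. Item 21 does not enter that calculation.

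**2. Share of follow-up after the last primary measurement.** With T weeks in study and the last sample at Week 8, the share is (T − 8)/T.

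| Weeks in study | Source | Share after Week 8 |
|---|---|---|
| 8 | stated minimum | 0/8 = 0% |
| 12 | Original Protocol: 8 weeks double-blind plus 4 open-label | 4/12 = 33% |
| 46 | projected average | 38/46 = 83% |
| 84 | stated maximum | 76/84 = 90% |

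The share passes one half when T exceeds 16 weeks.

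**3. From time to infections (assumption).** The documents give no COVID-19 incidence or timing. Assume a constant weekly hazard h = −ln(1 − I)/46, where I is the cumulative incidence by Week 46, and let F(x) = 1 − exp(−hx). The share of first positives after Week 8 is then [F(T) − F(8)] / F(T).

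| Assumed I | T = 12 | T = 46 | T = 84 |
|---|---|---|---|
| 5% | 33% | 82% | 90% |
| 10% | 33% | 82% | 90% |
| 20% | 33% | 81% | 89% |
| 30% | 32% | 80% | 87% |

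Under this assumption the share of infections is close to the share of time. Waves of infection, or early clustering, would break the link.

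**4. Which analysis would be run.** Item 21 fits two incompatible readings. Under SAP 2.5.9 as written, nobody is removed: a patient with any positive result moves to a complement level that the SAP does not name. If item 21 means an analysis restricted to COVID-free patients, there is one level and no interaction to test. The text does not say which is intended.

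**5. Comparison with sensitivity analysis 3.** For a patient first positive at Week 60, sensitivity analysis 3 keeps both the Week 4 and Week 8 values. For one first positive at Week 6, it drops Week 8 and keeps Week 4. Item 21 gives both patients the same label.

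**The case against.** The strongest reply is that the flaw is real but harmless. Conditioning on a post-randomization event distorts the treatment contrast only if positivity, or its detection, is related to treatment, directly or together with prognosis. The trial is double-blind and double-dummy, and neither document suggests that either drug affects infection. If infection is unrelated to treatment, the cost is mainly in precision and interpretation. This stands, and it is why no bias is claimed here.

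A reader might infer that most positives fall after the primary outcome was measured. The documents do not show this. The 83% is a share of follow-up time, it rests on the December 2019 projection, and across patients the share runs from 0% to about 90%.

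A reader might also infer that late positives are dropped from the Week 8 comparison. Under the interaction model they are reclassified, not dropped.

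Finally, item 21 is one of 22 items, changes neither the primary test nor the significance level, and overlaps with COVID-19 analyses already planned for the primary and secondary endpoints. That limits the damage. It also means that the item adds little: if a robustness check was intended, sensitivity analysis 3 already provides one with the right timing. None of these replies supplies a time limit or a complement, or turns the status into a baseline characteristic.

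**Conclusion.** The point holds as a minor one. Three facts follow directly from the text: item 21 is the only listed subgroup defined after randomization, it has no time limit, and it names no complement for the interaction test that SAP 2.5.9 requires. Followed as written, the plan classifies some patients by events that cannot have affected the Week 4/8 outcome, and it mixes infection with survival, length of follow-up and enrolment era. The resulting p-value is not a valid test of baseline effect modification.

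The extent depends on follow-up: none of a patient's time at risk lies after Week 8 at the minimum, a third at 12 weeks, about 83% at the projected average and about 90% at the maximum. Reading these as shares of infections requires a roughly constant hazard, which is an assumption.

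It would go too far to say that randomization is lost or that the treatment contrast is biased. That needs a link between positivity and treatment or prognosis which the documents neither state nor quantify. The primary analysis is unaffected.

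**What to change.** Either of two edits to the SAP is enough:

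1. **Preferred.** Delete item 21 from SAP 2.2.1 and rely on sensitivity analysis 3 for the primary endpoint, with the post-diagnosis censoring analyses in SAP 2.6.2 for the secondary endpoints.
2. **Alternative.** Move it to the supplementary analyses in SAP 2.5.8 as an analysis restricted to patients with no positive result up to the date of the last NT-proBNP sample used for that patient, with no interaction test. The actual sample date is better than Day 56 as the cut-off, because under Amendment 4 the Week 8 window in SAP 2.4.3 runs from Day 43 to Day 112.

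The first option costs one forest-plot row. The second costs a few lines of definition and programming. Neither loses patients or data, and neither changes the primary test or the sample size.

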## **2.3 Subject disposition, demographics and other baseline characteristics**

### **2.3.1 Subject disposition**

The number and percentage of subjects successfully screened will be presented. In addition, the reasons for screen failures will be provided. For subjects who are screened more than once, the information from the last screen will be used in the summary. This analysis will be performed on All subjects.

Number of subjects who were randomized will be presented on screen passed subjects.  
The following categories will be summarized on RAN:

- Number and percentage of subjects who were treated
- Number and percentage of subjects who prematurely discontinued study treatment during double-blind phase
- Number and percentage of subjects who prematurely discontinued study treatment during double-blind phase, excluding deaths
- Number and percentage of subjects who prematurely discontinued study treatment during open-label phase
- Number and percentage of subjects who prematurely discontinued study treatment during open-label phase, excluding deaths
- Reasons for premature discontinuation of study treatment (separately for double-blind phase and open-label phase)
  - Adverse Event
  - Death
  - Lost of Follow-Up
  - Study terminated by sponsor
  - Patient/Guardian decision
  - Protocol deviation
  - Physician decision
  - Pregnancy

Study duration in months [(date of last contact/death – date of first dose of study treatment + 1)/30.4375]

The following categories will be summarized by treatment group for the full study period (Baseline – Week 84 end)

- Subjects who received at least 1 dose of study treatment in the study period
- Subjects who did not receive at least 1 dose of study treatment in the study period and the reason

Furthermore, it will only be feasible to determine loss to follow-up at Week 84 end.

Subject disposition (total enrolled, total discontinued, total completed) by region (US and Canada) and pandemic phase will also be summarized for the RAN.

A summary of subjects who were randomized but did not meet the inclusion criteria #3, i.e. subjects enrolled outside of the respective protocol window will be provided. The summary will include subjects randomized with/without the protocol specified enrollment window (i.e., Original protocol 36H-10Days; Amendment 1-3 36H-30Days; Amendment 4 0H-30Days) by original protocol and amendments by treatment for RAN.

Additionally, listings of inclusion/exclusion criteria, screening disposition, reason for withdrawal of consent and study treatment disposition will be provided.

Any visit that did not occur per protocol will be listed with the reason it was not done.

### **2.3.2 Subject Protocol deviations**

The number and percentages of protocol deviations by category will be summarized. Additionally, a listing of protocol deviations during the study will also be presented. The FAS will be used.

In addition pandemic related protocol deviations will be summarized by category and relationship. All COVID-19 related protocol deviations will also be listed.

### **2.3.3 Qualifying Hospitalization/ED Visit/Out-of-Hospital Urgent HF**

The number and percentages of the following information about subjects and their qualifying hospitalization visit will be summarized by treatment group. The RAN will be used.

- Qualifying Healthcare Encounters
  - Hospitalization
  - Emergency Department (ED) Visit
  - Out-of-Hospital Urgent HF Visit
- Subject in shock (No, Yes, Unknown)
- Subjects receiving following treatment from qualifying hospitalization to randomization
  - Vasopressor (No, Yes, Unknown)
  - Inotrope (No, Yes, Unknown)
  - Nitroprusside (No, Yes, Unknown)
  - Nesiritide (No, Yes, Unknown)
  - IV Nitroglycerin (No, Yes, Unknown)
- Subject cared for in the intensive care unit (ICU) (No, Yes, Unknown)

The number and percentage (categorical variables) and descriptive statistics (continuous data) for information on subject qualifying hospitalization discharge will be summarized by treatment group. The RAN will be used.

- Duration of qualifying hospitalization stay in days [(date:time of discharge – date:time of arrival)/(3600\*24)]
- Discharge disposition (Home or with family/friends, Rehabilitation facility, Skilled nursing facility, Death, Unknown)
- Discharge weight (kg)
- NYHA class (I, II, III, IV)
- Subject experienced worsening HF since randomization (No, Yes, Unknown)
- Subject cared for in ICU (No, Yes, Unknown)
  - Number of nights in ICU since randomization
- Subject treated with any of the following medication classes since randomization (IV inotrope, IV vasopressor, Nitroprusside, IV Nitroglycerin,)

All information relating to the qualifying hospitalization will be listed.

With Amendment 4, not all subjects will have a qualifying hospitalization, with some qualifying based on a worsening HF event (e.g. ED visit or Urgent HF visit).

### **2.3.4 Demographics and other baseline characteristics**

Demographics, baseline characteristics, and disease history are collected at the screening visit. Descriptive summaries and/or listings will be provided. The number and percentage (categorical variables) and descriptive statistics (continuous data) for the information below will be summarized by treatment group for both double-blind and open-label subjects.

The FAS will be used. Summary statistics will be provided for Original Protocol subjects, and subjects recruited under the amended protocols, and all subjects in FAS.

In addition, demographics and baseline characteristics may be summarized by pandemic phases if needed.

